### 3.4 Week 12 Visit (70-120 days after Entry/Randomization Visit)

The SHUTi intervention and the internet sleep education/hygiene Active Control will be implemented between Entry/Randomization and Week 12. A UPT will be performed for women of reproductive potential; if positive, study participation will end and no further study procedures will be performed at this visit. Otherwise, once again, medical/psychiatric records, current medications, and current behavioral therapies will be reviewed and recorded. Weight and vital signs will be measured and recorded. All participants will complete a questionnaire battery containing the following: standard questions assessing demographics, medical/psychiatric history, sleep mediation use, insomnia treatment satisfaction, and insomnia care received outside of the trial; ISI; PSQI; DBAS-16; PHQ-9; SCL-20; GAD-7; PROMIS® Fatigue Short Form; AUDIT; PEG-3; and SF-36. The questionnaire battery will also include validated scales assessing physical activity level, tobacco use, illicit drug use, and medication adherence. The questionnaire battery will be administered on a computer in private with availability of the study team to assist only when asked by the participant. The participant may refuse to complete any of the questionnaire items.

We will then obtain again whole blood samples for laboratory testing of the inflammation biomarkers of interest and for updated HIV-1 RNA levels and CD4 cell counts. We will also archive blood and samples for future testing if consent for this is provided by the participant.

Participants who exhibit elevated depressive symptoms (PHQ-9  $\geq 10$ ) will be urged to follow-up with their primary HIV provider and/or clinical social worker regarding their depression.

### 3.5 Week 24 Visit/Closeout (150-210 days after Entry/Randomization Visit)

At this final/closeout study visit, a UPT will be performed for women of reproductive potential; if positive, study participation will end and no further study procedures will be performed at this visit. Otherwise, once again, medical/psychiatric records, current medications, and current behavioral therapies will be reviewed and recorded. Height, weight, and vital signs will be measured and recorded. All participants will complete a questionnaire battery containing the following: standard questions assessing demographics, medical/psychiatric history, sleep mediation use, insomnia treatment satisfaction, and insomnia care received outside of the trial; ISI; PSQI; DBAS-16; PHQ-9; SCL-20; GAD-7; PROMIS® Fatigue Short Form; AUDIT; PEG-3; and SF-36. The questionnaire battery will also include validated scales assessing physical activity level, tobacco use, illicit drug use, and medication adherence. The questionnaire battery will be administered on a computer in private with availability of the study team to assist only when asked by the participant. The participant may refuse to complete any of the questionnaire items.

We will then again obtain whole blood samples for laboratory testing of the inflammation biomarkers of interest and for updated HIV-1 RNA levels and CD4 cell counts. We will also archive blood and samples for future testing if consented by the participant.

Participants who exhibit elevated depressive symptoms (PHQ-9  $\geq 10$ ) will be urged to follow-up with their primary HIV provider and/or clinical social worker regarding their depression. In addition, the study team will notify the primary HIV provider that his/her patient has completed participation in our trial and if the participant still has clinically significant insomnia (ISI  $\geq 8$ ). The study team will also provide a list of local mental health services to the patients' primary HIV providers or social workers. After the procedures for this study visit have been performed, participation in this study will end, with no further active follow-up apart from notification of final study results.

### 3.6 Study Duration and Participant Retention

The maximum study period for each participant will be between 24 and 30 weeks, accounting for the 42-day period from Screening to the Entry Visit. To promote retention in the study, participants will be financially compensated at the Entry, Week 12, and Week 24 Visits.

#### 4.0 SELECTION AND ENROLLMENT CRITERIA

##### 4.1 Inclusion Criteria

- 4.1.1 HIV-1 infection, documented as listed clinically in the participant's electronic medical record by any of the following tests: (1) any licensed rapid HIV test, (2) HIV enzyme test kit at any time prior to study entry, (3) at least one detectable HIV-1 antigen, or (4) at least one detectable plasma HIV-1 RNA viral load.
- 4.1.2 Age equal to or greater than 18 years.
- 4.1.3 Ongoing receipt of stable antiretroviral therapy of any kind for at least 180 days prior to the date of the HIV-1 RNA value determining eligibility.
- 4.1.4 HIV-1 RNA level < 75 copies/mL at Screening.

NOTE: There are no CD4 cell count eligibility criteria for this trial.

- 4.1.5 ISI score  $\geq 11$  at Screening.

NOTE: Use of sleeping aids/medications is permitted as long as the ISI score criterion is met.

##### 4.2 Exclusion Criteria

- 4.2.1 Inability to complete written, informed consent.
- 4.2.2 Inability to read and understand English as seen on a computer screen.
- 4.2.3 Incarceration at the time of any study visit.
- 4.2.4 Active suicidality at Entry, as determined by the patient's HIV provider or social worker following a positive response (1, 2, or 3) to PHQ-9 Item #9 and a positive response (yes) to one or more of the three questions (for Question #3, the previous attempt must be within the past 10 years) on the Patient Suicidality Form (see Appendix).
- 4.2.5 Diagnosed disease or process, besides HIV infection, associated with increased systemic inflammation (including, but not limited to, systemic lupus erythematosus, inflammatory bowel diseases, or other collagen vascular diseases).

NOTE: Hepatitis B or C co-infections are NOT exclusionary, but treatment for hepatitis C cannot be provided during study participation.

- 4.2.6 End stage renal disease requiring renal replacement therapy (dialysis, transplantation).
- 4.2.7 Known or suspected malignancy requiring systemic treatment within 180 days of the Entry Visit.

NOTE: Localized treatment for skin cancers is not exclusionary.

- 4.2.8 Therapy for serious medical illnesses within 14 days prior to the Entry Visit.

NOTE: Therapy for serious medical illnesses that overlaps with a study visit will result in postponement of that study visit until the course of therapy is completed; postponement outside of the allowed study visit timeframe will result in study discontinuation.

- 4.2.9 Pregnancy or breastfeeding during the course of the study.
- 4.2.10 Receipt of investigational agents, cytotoxic chemotherapy, systemic immunosuppressive therapies, systemic glucocorticoids (of any dose), or anabolic steroids at the Entry Visit.

NOTE: Physiologic testosterone replacement therapy or topical steroids is not exclusionary. Inhaled/nasal steroids are not exclusionary as long as the participant is not also receiving HIV protease inhibitors.

- 4.2.11 Active drug use or dependence that, in the opinion of the investigator, would interfere with adherence to study requirements.
- 4.2.12 History of bipolar disorder or a psychotic disorder, including schizophrenia.

NOTE: Depressive disorders are not exclusionary.

- 4.2.13 Current sleep disorder diagnosis other than insomnia disorder (e.g., sleep apnea).
- 4.2.14 Have a schedule requiring a bedtime earlier than 8:00pm or later than 2:00am or arising time earlier than 4:00am or later than 10:00am (thus preventing adoption of SHUTi interventions).

If participants are excluded due to the above criteria, they may be approached again in the future or have their study visit rescheduled within the allowable timeframe if these criteria are no longer applicable.

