### 6.2.3 Medication/Supplement Use and Psychiatric Treatment History

A medication history must be present in source documents. The following information will be recorded on the CRFs at the Screening Visit:

- Start dates of current antiretroviral treatments
- Start dates of current insomnia and antidepressant treatments
- Any other prescription medications within 30 days of Entry Visit
- Any supplements (non-prescription) used within 30 days of Entry Visit
- Any behavioral treatments within one year of Entry Visit

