## 8.0 CRITERIA FOR STUDY DISCONTINUATION

- Request by the participant to withdraw
- Request of the primary care provider if s/he believes the study is no longer in the best interest of the participant
- If the participant is found to be pregnant or begins breastfeeding during the course of this study
- If the participant develops a fever, need for systemic therapy for acute or serious illness, or hypotension after screening that precludes completion of the study visits within the allowed timeframes
- Requirement for prohibited concomitant medication(s)
- Clinical reasons believed life threatening by the physician
- Participant, as judged by the investigators, to be at risk of failing to comply with the provisions of the study protocol as to cause harm to self

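### The 14-day interval after therapy for serious illness applies only before Entry, so Week 24 hsCRP can be drawn as soon as such therapy ends, adding avoidable noise to the primary endpoint

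*Protocol*

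**What the plan says.** Exclusion criterion 4.2.8 of the protocol reads "Therapy for serious medical illnesses within 14 days prior to the Entry Visit". It names the Entry Visit and no other.

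The NOTE beneath it covers every study visit but works differently. Therapy that overlaps a visit "will result in postponement of that study visit until the course of therapy is completed", and "postponement outside of the allowed study visit timeframe will result in study discontinuation". Section 8.0 adds a discontinuation criterion for fever, "need for systemic therapy for acute or serious illness, or hypotension after screening that precludes completion of the study visits within the allowed timeframes". None of these sets an interval between the end of therapy and the blood draw.

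Biomarker blood is taken at Entry, Week 12 and Week 24 (section 6.2.6.6). The visit windows are days 70 to 120 and days 150 to 210 (sections 3.4 and 3.5). The primary objective is the 24-week change in hsCRP (section 1.1.1), tested by ANCOVA of the Week 24 level adjusted for baseline (section 9.1 and the SAP's Statistical Analyses). Week 12 hsCRP is a secondary endpoint (section 1.2.1).

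Under section 9.13.2, and the matching SAP text on data cleaning, outliers that are not entry errors are kept in the primary analysis. Changing or removing them in a sensitivity analysis is optional. If normality fails, a transformation or nonparametric test is to be considered.

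**The concern.** hsCRP is a marker of systemic inflammation, and a serious illness that has just been treated is a plausible source of a raised value. The two rules treat the same event differently. A participant who finishes treatment the day before Entry must wait 14 days. One who finishes on day 167 can give the primary-endpoint sample on day 168.

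Adjusting for baseline cannot remove a disturbance that arises only at Week 24. With about 20 completers per arm and genuine outliers retained, a few such samples would widen the confidence interval, and an uneven split could move the estimated difference. That matters because the trial is meant to supply effect sizes for a later definitive trial (sections 2.4 and 9.5).

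**Working it through.** **1. Is there an interval elsewhere?** Sections 3.4, 3.5 and 6.2.6.6 are silent. Section 8.0 acts only when illness prevents a visit within its window. The closing text of section 4.2 allows rescheduling while an exclusion applies, but the 14 days in 4.2.8 are tied to Entry. The SAP has no rule for hsCRP drawn near an acute illness. After Entry, the interval is therefore zero days once therapy is complete.

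**2. The plan's own figure.** Inputs from section 9.5: SD 4.87 mg/L, correlation 0.64, 20 per arm, 80% power. Section 9.1 gives a two-sided alpha of 0.05.
- Residual SD = 4.87 × √(1 − 0.64²) = 3.74.
- Detectable difference by noncentral t with 37 degrees of freedom = 3.40 mg/L, against 3.41 stated. The figure reproduces.
- Detectable difference per unit of residual SD = 3.404 / 3.742 = 0.910.

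**3. One extra affected participant.** A rise of X mg/L in one more participant in one arm of 20 shifts the mean difference by X/20: 0.25, 0.5 or 1.0 mg/L for X = 5, 10 or 20. For scale, the earlier depression trial observed a difference of 1.18 mg/L (section 2.3.2, Table 1).

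**4. Loss of precision (illustration).** Assume a share p of Week 24 samples in both arms is raised by D mg/L. Neither value is in the documents.
- Residual SD becomes √(3.742² + p(1 − p)D²).
- Detectable difference = 0.910 × that SD.

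| p | D (mg/L) | Residual SD | Detectable difference (mg/L) |
|---|---|---|---|
| 2.5% | 5 | 3.82 | 3.48 |
| 2.5% | 10 | 4.05 | 3.69 |
| 5% | 5 | 3.90 | 3.55 |
| 5% | 10 | 4.33 | 3.94 |

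At p = 5%, power to detect 3.41 mg/L is about 77% for D = 5 and 68% for D = 10.

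**5. How demanding is p?** If illness timing is unrelated to the visit, p in a 14-day span implies p × 365/14 courses per person-year: about 0.65 for 2.5% and 1.3 for 5%. If postponement doubles the span to 28 days, the rates are about 0.33 and 0.65. These are fairly high.

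**6. Would the outlier screen catch it?** The threshold is a z score of 3.3. At SD 4.87 that is 3.3 × 4.87 = 16.1 mg/L above the mean, so a rise of 10 mg/L from an average level would not be flagged.

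**7. Does a 14-day interval fit?** From nominal days 84 and 168, 120 − 84 = 36 and 210 − 168 = 42 days remain. The full interval fits if therapy ends by day 120 − 14 = 106 or day 210 − 14 = 196.

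**The case against.** Four objections carry weight.

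- **The gap is narrow.** The NOTE already prevents draws during therapy, and sections 5.3 and 8.0 remove participants who need prohibited drugs. Non-serious acute illness is screened at no visit, Entry included. A reader might infer that baseline is protected and the endpoint is not. That is too broad: the difference concerns only the period just after completed therapy for a serious illness.
- **The purpose of the 14 days is inferred.** No section links them to hsCRP. The inference is reasonable for an inflammation endpoint, but it remains an inference.
- **The size is unknown.** The illness share and the rise are assumptions, and the implied illness rates are high for a cohort that excludes inflammatory disease, dialysis and recently treated malignancy. The SD of 4.87 comes from an earlier trial and may already include such values.
- **Consequences are limited.** Section 9.5 says the sample is not sized for definitive superiority testing, and section 9.13.2 leaves room for transformation, nonparametric tests and outlier sensitivity analyses. These are discretionary and would not reliably pick out the affected samples.

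A reader might also see a matching gap in 4.2.10, which bars "systemic glucocorticoids (of any dose), or anabolic steroids at the Entry Visit" with no look-back. The documents do not support adding it. Therapy for a serious illness already falls under 4.2.8, malignancy treatment under 4.2.7, and diagnosed inflammatory disease under 4.2.5. The history that would supply the look-back, "Any other prescription medications within 30 days of Entry Visit", is recorded at Screening (section 6.2.3), which may be weeks before Entry.

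These points limit the size of the concern. The difference between the two rules stands.

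**Conclusion.** The point holds as a modest, cheaply corrected weakness. Week 24 hsCRP can be drawn immediately after therapy for a serious illness, while the Entry sample cannot, and neither document says how such a sample is handled. Only Week 24 bears on the primary endpoint.

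A reader might infer that the treatment comparison is biased. The documents do not support that: under randomization the expected effect is extra variance and chance imbalance, unless illness differs by arm, and nothing in the plan suggests it does. Nor do they show that the stated 3.41 mg/L is wrong. It reproduces, and the move to about 3.5 to 3.9 mg/L rests wholly on the assumed 2.5 to 5% of samples raised by 5 to 10 mg/L. If the planning SD already contains such values, there is no inflation above 3.41, and the fix would bring an unquantified gain in precision instead.

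**What to change.** Reconcile the NOTE in 4.2.8 with its Entry criterion, so that the Week 12 and Week 24 blood draws observe the same interval after the end of therapy as Entry does, within the existing windows of days 70 to 120 and 150 to 210.

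If therapy has ended but the interval cannot be reached before the window closes, draw within the window, keep the sample in the intention-to-treat analysis, and flag it. Add to the SAP a prespecified sensitivity analysis for flagged samples. Prescription stop dates since Entry are already recorded (section 6.2.5), so flagging should need little or no new data collection.

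Leave the existing rule for therapy that runs past the window unchanged. The amendment then discontinues no one who would otherwise have stayed.

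The cost is a wording amendment and a few visits up to two weeks later. The sleep diaries for the 14 days before each visit (section 5.2) move with them, and a visit near the end of its window leaves less room for rebooking.

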## 5.0 STUDY TREATMENTS

5.1 The Intervention Group: SHUTi. SHUTi is the empirically supported, internet CBT-I created by our consultant, [name], that is fully accessible via tablets and smartphones. It uses a self-guided, fully automated, interactive, multimedia format to deliver six 45-minute sessions, the structure and content of which mirror traditional face-to-face CBT-I (96, 97). Session content includes sleep restriction, stimulus control, sleep hygiene, cognitive restructuring, and relapse prevention. The primary model of behavior change on which SHUTi is based is Social Cognitive Theory, the most widely used model of behavior change in the internet intervention literature (98). Each session has the same structure: objectives, sleep diary and homework review, new intervention material, homework assignment, and summary. Session content was created to be engaging and is based on learning theory and instructional design (99). SHUTi is enhanced through a variety of interactive features, including personalized goal setting, graphical feedback based on inputted symptoms, animations and illustrations to enhance comprehension, quizzes to test user knowledge, patient vignettes, and video-based expert explanation. Across sessions, patients also receive tailored sleep recommendations and feedback based on the sleep diary data they enter into the program. SHUTi has been shown to be acceptable, feasible, and effective in several RCTs published in high-impact journals (87, 100-103) with effect sizes comparable to face-to-face CBT-I (79).

SHUTi was developed and studied in patients who were 18 years and older (100, 102). The prescription digital therapeutic platform for chronic insomnia marketed as Somryst™ utilizes SHUTi principles but carries an FDA approval only for those aged 22 and greater, as the FDA considered those under age 22 (e.g. ages 18-21) to be children and would thus require a separate pediatric indication using pediatric insomnia measures. As this study will use SHUTi (which is licensed for research purposes by [name] group for those 18 and older), and not Somryst™, we will include HIV-positive patients with insomnia who are 18 years or older to increase external generalizability and extend the study's potential impact across the lifespan as per our NIH application.

To minimize treatment barriers, attrition, and subject burden, SHUTi sessions will be delivered remotely at a location selected by the participant where s/he can access a computer with internet, such as the participant's

home, the participant's work, a family member's/friend's home, or a public library. We will loan study tablet computers with data plans to patients without reliable internet access to maximize intervention update and decrease attrition. [name] laboratory and the Infectious Diseases Research Clinic at Eskenazi Health Hospital will serve as backup locations for SHUTi session delivery if a participant prefers in-person delivery.

We will deliver SHUTi with support, as it increases the efficacy of internet interventions (104-106). Specifically, the Intervention RA, a clinical psychology PhD mentee of [name], will track each participant's progress through the SHUTi dashboard and will check-in with each participant every two weeks to address any questions or issues.

We will also tell patients that, if they choose to complete SHUTi session where others are present, these other people (e.g., family member or friend) may realize that they are completing a treatment for insomnia. It will be up to each patient to decide if the available remote locations provide sufficient privacy. Up to 6 sessions will be completed by the participant between the Entry Visit and the Week 12 Study Visit at rate of a session every 1-2 weeks. No physiologic or biologic assessments will be performed during these sessions. The participants need not be fasting for these sessions.

Information is collected by the SHUTi program while it is being used by participants, which the program requires to tailor interventions to each participant's particular sleep problem. Of note, participants in our trial will not enter any identifying information into the SHUTi program other than the email address they choose to use to receive messages (e.g., reminders) from the program. They will also enter information related to their current sleep problem (sleep diary, insomnia symptoms, and treatment goals) and will be identified by a unique participant ID number and a unique password. The key linking participant names with their SHUTi login information will be kept in a separate secure and locked file cabinet. All data collected through SHUTi will be saved on password-protected computers and secure servers. In addition, the SHUTi program's data security and storage at the University of Virginia was reviewed by the Indiana University Committee of Data Stewards and was approved on October 7, 2021 (Request ID#: 00010559). Thus, the data entered into SHUTi is highly protected.

## 5.2 The Active Control Group: Internet Sleep Education/Hygiene, Symptom Monitoring, and Usual Care.

In our pilot trial, our comparator was usual care. However, in the proposed trial, we will use an active control comparator (107) for two reasons. First, we wish to obtain precise effect size estimates for the next-step trial, and a usual care comparator could overestimate efficacy. Of note, Irwin's RCT (21) found moderate-to-large improvements in insomnia remission and CRP with CBT-I versus a sleep education/hygiene active control. Second, our active control arm will help to ensure that the groups have similar expectancy of benefit.

The Active Control RA, another clinical psychology PhD mentee of [name], will oversee and deliver the active control procedures. First, the RA will give participants access to the internet sleep education/hygiene program, which was created by our consultant, [name], to serve as a standardized active control condition for SHUTi. This educational program was developed at the University of Virginia with funding from the National Institutes of Health and is fully accessible via tablets and smartphones. This program provides static information about: insomnia symptoms; the impact, prevalence, and causes of insomnia; when to see a doctor; and basic lifestyle, environmental, and behavioral strategies to improve sleep (i.e., sleep hygiene recommendations). Of note, participants in our trial will not enter any identifying information into the internet sleep education/hygiene program other than the email address they choose to use to receive messages (e.g., reminders) from the program. The content for this program was informed based on a review of insomnia-focused websites at the time of development. Second, just after giving participants access the internet sleep education/hygiene program, the RA will email or mail a list of local behavioral health services to patients and will encourage them to follow-up with their HIV provider. To engender expectancy of benefit, the RA will stress that our notifications should prompt actions by their provider and that the available treatments are evidence-based. We will then notify the HIV provider, which will encourage them to address their patient's

insomnia and provide the same list of local services. The same RA will also call each control participant every 4 weeks to assess insomnia symptoms (ISI) and will notify clinical staff to encourage additional care when indicated. Furthermore, the RA will encourage continued use of the sleep hygiene practices. Each control participant will receive usual primary care for insomnia, which in our local HIV clinics is typically limited to sleep hygiene practices (CBT-I is not offered) and use of antihistamines and trazodone (hypnotics and benzodiazepines are rarely used).

Participants randomized to either the Intervention group or the Active Control group will complete sleep diaries based on consensus sleep diary questions (108) that are incorporated into the online platforms for SHUTi and Active Control for the 14 days immediately after the Entry visit and the 14 days immediately before the Week 12 and Week 24 visits.

We will also assess treatment credibility/expectancy of benefit (109) (end of first SHUTi session or active control call) and insomnia treatment satisfaction with an item from our past trials (Week 12 Visit).

Of note, there will be no restrictions on the care that the participants can receive by their primary care providers, although we will assess changes in such care during the trial.

